Protocol Synopsis

Title:

Neoadjuvant Chemoradiotherapy and Adjuvant Chemotherapy with 5-Fluorouracil and Oxaliplatin versus 5-Fluorouracil Alone in Rectal Cancer

This study is ongoing but not recruiting participants.

Study Start Date: July 2006

Primary Completion Date: October 2011

Estimated Study Completion Date: December 2014

Sponsor:	University of Erlangen-Nürnberg Medical School
Information provided by:	University of Erlangen-Nürnberg Medical School
ClinicalTrials.gov Identifier:	NCT00349076
Principal investigator	[name]., Dept. of Radiation Therapy/ Radiooncology, University of Erlangen, [name] [contact], [contact]

1. Selection of Patients, including both Eligibility and Ineligibility Criteria

Patients matching all inclusion criteria and none of the exclusion criteria listed below will be recruited in 88 participating centers.

Inclusion Criteria:

- Males and females aged ≥ 18 years, inclusive, at screening
- Histologically proven, advanced primary carcinoma of the rectum (tumor > 12 cm above the anal verge), with clinically staged T3/4 or any node-positive disease
- No prior cancer-specific therapy except a diverting stoma
- ECOG PS ≤ 2
- Adequate bone marrow function: Leukocytes $> 3,5 \times 10^9/L$, absolute Neutrophil count $> 1,5 \times 10^9/L$, Platelet count $> 100 \times 10^9/L$, Hemoglobin > 10 g/dL
- Adequate hepatic function: Total bilirubin $< 2,0$ mg/dL ALAT, ASAT, alkaline phosphatase, gamma-GT $< 3 \times$ ULN 7. Serum creatinine $< 1,5$ mg/dL, creatinine clearance > 50 mL/min
- Written informed consent by the competent patient

Exclusion Criteria:

- Pregnant or breast feeding women
- Fertile patients without adequate contraception during therapy
- Past or ongoing drug abuse or alcoholic excess
- Prior application of chemotherapy
- Prior application of radiotherapy to the pelvis
- Prior (within 4 weeks) or concurrent treatment with any other investigational agent
- Psychological, familial, sociological or geographical condition potentially hampering compliance with the study protocol and follow-up schedule
- History of severe somatic or psychological diseases: - instable cardiac disease not well controlled with medication, myocardial infarction within the last 6 months:* Central nervous system disorders or psychiatric disability including dementia or epileptic disease; * active uncontrolled intercurrent infections or sepsis
- Peripheral neuropathy > 2 (NCI CTC AE grading)
- Previous or concurrent malignancies, with the exception of adequately treated basal cell carcinoma of the skin or in situ carcinoma of the cervix. The inclusion of patients with other adequately treated tumors within the last 5 years has to be discussed with the principal investigator
- Chronic diarrhea (> 2 NCI CTC AE-Grade 1)
- Known allergy to substances containing platinum compounds
- Concurrent use of the antiviral agent sorivudine or chemically related analogues
- Known dehydropyrimidinhydrogenase (DPD) deficiency

2. Schema and Treatment Plan, including Administration Schedule

2.2 Schedule of Events

2.2.1 Pre-Treatment

Informed Consent

Informed Consent is obtained prior to any study-specific screening procedures.

Screening:

Assessment of eligibility to ensure all inclusion- and none of the exclusion criteria are met.

Randomization:

Random treatment assignment is performed centrally and is stratified by study center, clinical T-category (cT1-3/cT4), and clinical N-category (cN0/cN1-2).

2.2.2 Treatment

Arm A (Experimental):

Preoperative Radiotherapy

Radiotherapy consists of 28 daily fractions; single dose: 1.8 Gy per day, Monday through Friday, for 5 weeks. Total dose: 50.4 Gy, delivered with a minimum of 6 MV photons through a three- or four-field box technique to the primary tumor, mesorectal, presacral and internal iliac lymph nodes up to the level of the promontorium.

Preoperative Concurrent Chemotherapy

Concurrent chemotherapy with Oxaliplatin, Calciumfoliat and Fluoruracil: 5-Fluorouracil: 250 mg/m²/d by continuous intravenous (civ) infusion, Days 1-14 and 22-35; Oxaliplatin: 50 mg/m² intravenous (iv) infusion, Days 1, 8, 22 und 29.

Recovery

There is a recovery period of 5-6 weeks after chemoradiotherapy.

Surgery

Total mesorectal excision is performed according to a standardized technique.

Recovery

There is a recovery period of 4 weeks after surgery.

Adjuvant Chemotherapy

Oxaliplatin: 100 mg/m² iv on day 1; calciumfolinat: 400 mg/m² on Day 1; 5-Fluorouracil: continuous intravenous (civ) infusion of 2400 mg/m² over 46 hours; repeat Day 15, 8 cycles.

Arm B (Active Comparator):

Preoperative Simultaneous Radiotherapy

Radiotherapy consists of 28 fractions; single dose: 1.8 Gy once per day, Monday through Friday, for 5 weeks. Total dose: 50.4 Gy. Radiotherapy is delivered with a minimum of 6 MV photons through a three- or four-field box technique to the primary tumor, mesorectal, presacral and internal iliac lymph nodes up to the level of the promontorium.

Preoperative Concurrent Chemotherapy:

Concurrent chemotherapy with Fluorouracil: Administration during Week 1 and 5 of preoperative radiotherapy: civ infusion over 120 h with 1000 mg/m² (on Days 1-5 and 29-33), 4 cycles

Recovery

There is a recovery period of 5-6 weeks after chemoradiotherapy.

Surgery

Total mesorectal excision is performed according to a standardized technique.

Recovery

There is a recovery period of 4 weeks after surgery.

Adjuvant Chemotherapy

5-Fluorouracil: 500 mg/m² on 5 consecutive days (day 1-5) iv bolus for 2-5 minutes; repeat on Day 29, 4 cycles.

2.2.3 Assessment of Safety

During therapy, patients are monitored weekly for signs of acute toxic effects, with appropriate adjustments in chemotherapy and radiotherapy made as necessary. Assessment of perioperative and 30-day postoperative complications included anastomotic leakage, perineal complications, bleeding, ileus, fistulas, and death.

2.2.4 Follow-up

Over a follow-up period of 5 years, long-term toxic effects are assessed at 1, 3, and 5 years post treatment. Evaluations consist of physical examination, a complete blood count, and blood chemical analysis. Proctoscopy, abdominal ultrasonography, CT of the abdomen, and chest radiography are also used, according to guidelines of the German Cancer Society.[1] Histopathological confirmation of local recurrence (defined as a tumor within the pelvis or the perineal scar) and of distant recurrence is encouraged; acceptable alternative approaches included sequential radiologic studies to detect the enlargement of a mass. The physicians evaluating patients' relapse status are aware of the treatment assignments.

3. Rules for Dose Modification

3.1 Toxicity and Adverse Events

Acute toxicity will be assessed according to the NCI Common Terminology Criteria for Adverse Events, v 3.0 (CTC AE). In case of adverse events which do not result in severe or life-threatening consequences as judged by examining physician (e.g. alopecia), treatment should not be modified. If several different kinds of toxicity occur, the most vigorous dose reduction step should be applied.

If an adverse event can be traced back exclusively on one cytostatic agent or specifically on the radiotherapy (e.g., hand-foot syndrome by continuous 5-FU infusion, neurotoxicity by oxaliplatin) the dose of the other drug or of radiotherapy does not have to be modified. If dose reduction becomes necessary, the reduced dosage will be kept until end of pre-operative chemoradiotherapy or of adjuvant chemotherapy, respectively. A new escalation is not allowed. If toxicity requires therapy interruption of more than two weeks, the patient will be removed from the study for toxicity reasons.

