4.2 Secondary Endpoints

- Resection rate
- rate of sphincter preservation
- tumor regression
- cumulative incidence of local and distant recurrences
- overall survival
- toxicity
- quality of life

5. Reasons for early Cessation of Trial Therapy

If toxicity requires therapy interruption of > 2 weeks, the patient will be removed from the study for toxicity reasons.

Throughout the study, patients may be subject to medical assessment and review of compliance before continuing in the study. Patients must continue to meet the inclusion and exclusion criteria during the study, including restrictions related to contraception, if applicable, and medication use. Noncompliant patients may be discontinued from the study.

Every patient will be informed that participation in the study is voluntary and that consent can be withdrawn at any time without the need to provide reasons, and without disadvantage or prejudice.

6. Objectives and Entire Statistical Section (Including Endpoints)

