6.1. Statistical Endpoints and Hypothesis

Primary endpoint:

To show superiority of the addition of oxaliplatin to neoadjuvant chemoradiotherapy (N-CRT) and to 5-FU-based adjuvant chemotherapy (experimental arm) in comparison to standard N-CRT followed by adjuvant 5-FU monotherapy (control arm) in terms of DFS within three years of follow-up (primary endpoint).

DFS is defined as the time frame between day of randomization and the first day of occurrence of at least one of the following items:

- R2 resection
- local relapse following R0 or R1 resection
- evidence of distant metastasis
- death of the patient

If none of the aforementioned events occur for a randomized patient within the follow-up time, the patient will be censored at the first day at which at least one of the following events occur:

- end or truncation of the study
- study dropout by patient's initiative

The null hypothesis of this study is that there is no statistically significant difference between the experimental and the control arm.

Secondary endpoints were classified as:

- R0 resection rate, circumferential resection margins, quality of TME-surgery
- TNM-classification, number of investigated lymph nodes after quality controlled TME-surgery
- proportion of sphincter-preserving surgical procedures
- tumor regression grading
- cumulative incidence of local relapses and distant metastasis
- overall survival after five years
- acute toxicity of radio- and chemotherapy according to CTC criteria
- late toxicity of radio- and chemotherapy

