6.3 Analysis cohorts

The 'intent-to-treat' population refers to all randomized patients with the study arm defined by randomization, regardless of protocol violations, stop of treatment, or time of follow-up.

The 'per-protocol' population is composed of all patients who started therapy. The patients will be analyzed in the therapy arm where they were actually treated, regardless of randomization. For the interim safety analyses all randomized patients will be considered who started therapy.

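### The protocol removes patients from the study for toxicity or noncompliance without saying that DFS follow-up continues, which leaves room for informative censoring that plausibly differs by arm

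*Protocol*

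**What the plan says.** Section 3.1 (Toxicity and Adverse Events) closes with the rule "If toxicity requires therapy interruption of more than two weeks, the patient will be removed from the study for toxicity reasons". Section 5 gives it again in nearly the same words: "If toxicity requires therapy interruption of > 2 weeks, the patient will be removed from the study for toxicity reasons". That section carries the title "Reasons for early Cessation of Trial Therapy". It adds that "Noncompliant patients may be discontinued from the study" and that "Patients must continue to meet the inclusion and exclusion criteria during the study", the latter with explicit reference to contraception and medication use.

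On the analysis side, 6.3 defines the intention-to-treat population as "all randomized patients with the study arm defined by randomization, regardless of protocol violations, stop of treatment, or time of follow-up", and 6.4.1 bases the primary log-rank test on it. Section 6.1 says when a patient without a DFS event is censored. It gives two reasons: the end or truncation of the study, and dropout on the patient's own initiative ("study dropout by patient"). Removal by the investigator is not among them.

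No section says whether a patient removed under 3.1 or 5 continues to be followed for DFS.

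**The concern.** An intention-to-treat analysis of a time-to-event endpoint needs more than a list of who counts. It also needs their outcomes after treatment stops. A centre that takes the removal wording at face value may end follow-up on the day the patient leaves, and with 88 centres practice could vary. The rule acts during therapy, early in DFS time, so most of such a patient's DFS experience would go unobserved.

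If those patients had the same prognosis as everyone else, only some events would be lost. Patients whose toxicity interrupts therapy for more than two weeks may well do worse, however, and the protocol itself expects more toxicity in the oxaliplatin arm. Worse prognosis together with more removals in Arm A would take proportionally more high-risk patients out of Arm A's follow-up and make Arm A look better than it is.

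**Working it through.** **1. The texts side by side.**

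- Sections 3.1 and 5 use study-level wording for the exit.
- Where the protocol means treatment only, it says so: 3.2 stops chemotherapy at grade IV toxicity, and 3.4 stops the entire chemotherapy if 5-FU must be discontinued.
- Section 6.1 offers no censoring reason that fits an investigator's removal. Sections 6.3 and 6.4.1 need the patient's DFS all the same.
- The four provisions fit together only if removal ends treatment and follow-up goes on. That is not stated.

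**2. The plan's own sample size (6.2).** Inputs: 3-year DFS 74.9% and 82%, 3 years' accrual, 2 years' minimum follow-up, 5% protocol violations per arm, 5% level (taken as two-sided), 80% power.

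- Exponential hazards: −ln(0.749)/3 = 0.0963 and −ln(0.82)/3 = 0.0662 per year. HR = 0.0662/0.0963 = 0.687.
- Lachin–Foulkes gives N = 927 without violations. Treating 5% violations in each arm as crossover gives 927/(1 − 0.05 − 0.05)² ≈ 1144.
- At N = 1200, power is about 82%, so the stated figure of about 1200 is broadly reproduced.
- Expected events: 600 × (0.284 + 0.205) = 293.

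**3. Loss of power if follow-up ended at removal.** Assumptions: removal at 0.4 years and the removal rates shown. Power = Φ(|ln HR|·√D/2 − 1.96), with D the number of events and the HR diluted to 0.713 by the 5% violations.

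| Removed, control / experimental | Events | Power |
|---|---|---|
| none | 293 | 82.4% |
| 2% / 5% | 285 | 81.3% |
| 5% / 10% | 275 | 80.0% |
| 5% / 20% | 265 | 78.4% |

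The loss is small. Bias is the larger risk.

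**4. Bias with no true effect.** Each arm has 3-year DFS of 74.9%. A fraction f is removed and has k times the hazard λ of the rest, where λ solves

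(1 − f)·exp(−3λ) + f·exp(−3kλ) = 0.749.

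For f = 10% and 4% with k = 2, λ = 0.0885 in Arm A and 0.0931 in Arm B.

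Removed patients contribute follow-up until an assumed 0.4 or 0.5 years and are then censored. From the expected log-rank O − E and variance V, z = (O − E)/√V, and the chance of wrongly declaring Arm A better is Φ(−1.96 − z). In the central case at 0.4 years, O − E = −3.25 and V = 76.8, so z = −0.37 and the chance is Φ(−1.59) = 5.6%.

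| Removed, A / B | k | Apparent HR (0.4; 0.5 y) | Chance of falsely favouring A (0.4; 0.5 y) |
|---|---|---|---|
| 5% / 2% | 1.5 | 0.988; 0.989 | 3.2%; 3.2% |
| 10% / 4% | 2 | 0.959; 0.960 | 5.6%; 5.4% |
| 15% / 5% | 3 | 0.889; 0.894 | 16.6%; 15.5% |
| 10% / 4% | 1 | 1.00; 1.00 | 2.5%; 2.5% |

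The nominal value is 2.5%. A simulation with censoring at 0.4 years gave about 3.5%, 5.8% and 17% for the first three rows, which agrees.

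**5. Sensitivity to the time of removal.** Dropping removed patients from time zero gives larger effects. The central case becomes HR 0.0885/0.0931 = 0.951. With about 301 events the shift is 0.051 × √301/2 = 0.44 and the chance 6.4%. The upper case becomes HR 0.865 and 22% with about 272 events. Time zero is not realistic, because the rule operates only once treatment is under way, so the table above is the fairer illustration.

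**The case against.** The strongest reply is that the rule concerns therapy only. It stands under the headings for dose modification and for early cessation of trial therapy, and no sentence says that follow-up stops. Section 6.1 can even be read in support: since removal is not a censoring reason, a removed patient without an event would run on to the end of the study, which presupposes continued follow-up. Much of this stands. It makes loss of outcomes an inference rather than a stated rule. It does not settle the matter, because 3.1 and 5 name the study and not the therapy, and Section 5 also covers withdrawal of consent, which is a study-level exit.

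Four stronger readings are tempting, and the protocol does not support them:

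- *The rule contradicts intention-to-treat.* Membership of the population is safe, since 6.3 keeps every randomised patient "regardless of protocol violations, stop of treatment, or time of follow-up". What is at risk is the collection of their outcomes.
- *Removals will certainly be more frequent in Arm A.* Section 6.4.4 ties the expected excess to oxaliplatin neurotoxicity. Under 3.1 the other drug need not then be modified, and under 3.4 treatment goes on with 5-FU if oxaliplatin is stopped for good. Not every such toxicity therefore interrupts all therapy. Section 3.4 also postpones both drugs when a cycle is delayed, so an imbalance remains plausible.
- *Every treated patient breaches the continuing-eligibility sentence because chemotherapy is an exclusion.* That criterion plainly refers to treatment before entry.
- *A removed patient has no censoring date at all.* On the treatment-only reading, 6.1 supplies one.

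**Conclusion.** The point holds as an unresolved conflict in wording that bears on the primary endpoint. Sections 3.1 and 5 take patients out of the study and do not keep them in DFS follow-up. Followed literally, this ends observation for a reason that 6.1 does not list and weakens the comparison that 6.3 and 6.4.1 rely on. The protocol does not show that outcomes will be lost, or that the loss will differ by arm.

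The size depends wholly on assumed removal rates, hazard multiples and removal times. Over the range examined, with no true effect, the apparent HR runs from about 0.99 to about 0.89. The chance of wrongly favouring Arm A runs from about 3% to about 15–17%, and the central case is about 0.96 and 5–6%. If removed patients have the same prognosis as the others there is no bias, only a modest loss of power. The direction favours Arm A only if removals are more frequent there and removed patients do worse. An amendment is justified because it is cheap and protects the primary comparison on either reading.

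**What to change.** Reconcile Sections 3.1, 5, 6.1 and 6.3 by stating that:

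- removal for toxicity or noncompliance ends study treatment only;
- the patient stays on the planned follow-up schedule for DFS, overall survival and late toxicity;
- follow-up ends early only by withdrawal of consent or loss to follow-up, and the censoring list in 6.1 matches this;
- the continuing-eligibility sentence in Section 5 governs study treatment and cannot end follow-up. It should be kept, because it carries the contraception and medication restrictions.

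The two-week rule is a clinical matter and is left untouched. The cost is a short amendment and the continuation of follow-up visits that are already planned, now also for patients who are off treatment.

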6.4 Statistical Analysis

6.4.1 Testing the Primary Endpoint

The hypothesis concerning the primary endpoint, as defined in Section 6.1, is based on the 'intent-to-treat' population assessed by log-rank statistics. The reference distribution under the null hypothesis of equal DFS in both arms will be derived from the asymptomatic conditional distribution of the log-rank statistics for each participating center and in relation to the most prognostic factor, the lymph node status at time of randomization. That corresponds to stratification according to participating centers and dichotomous lymph node status. The effect size is defined by the point estimator with 95% confidence interval of the hazard ratio. If the null hypothesis can be rejected at level of 5%, the experimental treatment will be established. The primary endpoint will be visualized by Kaplan-Meier survival curves.

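### Removal of patients 'from the study' for long toxicity interruptions or noncompliance is not reconciled with an intent-to-treat DFS analysis that needs their follow-up

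*Protocol*

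**What the plan says.** Section 3.1 (Toxicity and Adverse Events) states: "If toxicity requires therapy interruption of more than two weeks, the patient will be removed from the study for toxicity reasons". Section 5 repeats it almost word for word: "If toxicity requires therapy interruption of > 2 weeks, the patient will be removed from the study for toxicity reasons". It then adds: "Noncompliant patients may be discontinued from the study". The heading over Section 5 is "Reasons for early Cessation of Trial Therapy".

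Section 6.3 keeps every randomised patient in the assigned arm "regardless of protocol violations, stop of treatment, or time of follow-up". Under Section 6.4.1 the primary hypothesis "is based on the 'intent-to-treat' population assessed by log-rank statistics". Section 6.1 gives two reasons for censoring a patient without an event: "end or truncation of the study" and "study dropout by patient's initiative".

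Section 2.1 sets follow-up visits every 3 months for 2 years and every 6 months for 3 more. Section 2.2.4 describes the examinations and the late-toxicity assessments at 1, 3 and 5 years. Neither says whether a patient removed under Section 3.1 or 5 stays on this schedule.

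**The concern.** A site that follows Sections 3.1 and 5 to the letter has grounds to stop collecting outcomes once a patient is removed. The protocol uses different words when it means only treatment: Sections 3.2 and 3.4 speak of chemotherapy being stopped. Section 5 also uses the word study for a patient's participation as a whole.

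The analysis sections presuppose the opposite. An intent-to-treat log-rank test that disregards treatment stops needs DFS to be observed after the stop. The censoring list has no entry for a patient taken out by rule.

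Three things are at stake:
- Events, and so power, in the primary comparison.
- The balance of the comparison. Section 6.4.4 expects a trend to higher toxicity grades with oxaliplatin, so a toxicity-driven rule may act more often in Arm A.
- Late toxicity, a secondary endpoint, for which patients with serious acute toxicity are of particular interest.

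**Working it through.** **1. The passages side by side**

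| Question | Sections 3.1 and 5 | Sections 6.1, 6.3, 6.4.1 |
|---|---|---|
| Is the patient in the analysis set? | Removed from the study | Yes, whatever the treatment stop or follow-up time |
| Is DFS observed after removal? | Literally no; under the Section 5 heading, perhaps yes | Needed until an event, study end or the patient's own dropout |
| How is the patient censored if follow-up ends? | Not stated | Removal by rule is not a listed reason |

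The conflict is therefore over outcome data and censoring. Membership of the intent-to-treat set is not in question.

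**2. The plan's own figure**

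Inputs from Section 6.2: 3-year DFS 74.9% and 82%, 5% protocol violations per arm, 3 years' recruitment, 2 years' minimum follow-up, 1200 patients. Assumed: exponential DFS, two-sided 5%, violations acting as crossover.

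- Hazards: -ln(0.749)/3 = 0.0963 and -ln(0.82)/3 = 0.0662; ratio 0.687.
- After 5% crossover: 0.95 x 0.0963 + 0.05 x 0.0662 = 0.0948, and 0.95 x 0.0662 + 0.05 x 0.0963 = 0.0677; ratio 0.713.
- Event probability 1 - (e^(-2h) - e^(-5h))/(3h): 0.280 and 0.210, so about 294 events in 1200 patients.
- Power: sqrt(294) x |ln 0.713|/2 - 1.96 = 0.93, which is 82.5%.
- Required N is 1128-1148, or 1187-1208 if also divided by 0.95. About 1200 is attainable.

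**3. Events and power if removal ends follow-up**

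Assumed: removal at 0.5 years, same hazard as the rest. The event probability in an arm with fraction r removed is (1 - r) x p + r x (1 - e^(-0.5h)), where p is that arm's event probability from step 2.

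| Removed, Arm A / Arm B | Events | Power |
|---|---|---|
| 0 / 0 | 294 | 82.5% |
| 5% / 2% | 286 | 81.4% |
| 10% / 5% | 276 | 80.1% |
| 15% / 5% | 271 | 79.3% |
| 20% / 10% | 259 | 77.5% |

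**4. Bias with no true effect, closed form**

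Assumed: true 3-year DFS 74.9% in both arms; removal at 0.5 years in Arm A only; removed patients have m times the hazard of the rest. Solve (1 - r)e^(-3h) + r e^(-3mh) = 0.749 for h. The Kaplan-Meier estimate at 3 years is then [(1 - r)e^(-0.5h) + r e^(-0.5mh)] x e^(-2.5h).

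Example with r = 10%, m = 2: h = 0.0885, estimate = 0.9526 x 0.8016 = 0.7636, which is 1.46 points too high. The equivalent hazard ratio is ln(0.7636)/ln(0.749) = 0.933.

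| r in Arm A | m = 1 | m = 1.5 | m = 2 | m = 3 |
|---|---|---|---|---|
| 5% | 1.00 | 0.98 | 0.97 | 0.94 |
| 10% | 1.00 | 0.96 | 0.93 | 0.89 |
| 15% | 1.00 | 0.95 | 0.90 | 0.84 |

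The largest overstatement in this table is 3.5 points, against a planned difference of 82 - 74.9 = 7.1 points.

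**5. Bias with some removal in both arms, simulation**

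Assumed: 600 per arm, no true effect, 15% frail patients with m times the hazard, removals drawn from the frail at 0.45 years, 2,500 trials per scenario, about 338 events without removal.

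| Removed, Arm A / Arm B | m | Hazard ratio | Events lost | Two-sided error |
|---|---|---|---|---|
| 10% / 5% | 1.5 | 0.983 | 28 | 5.1% |
| 10% / 5% | 2 | 0.964 | 33 | 6.7% |
| 15% / 5% | 1.5 | 0.965 | 37 | 6.1% |
| 15% / 5% | 2 | 0.934 | 44 | 8.7% |

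Events lost are 28/338 = 8% to 44/338 = 13%.

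**The case against.** The strongest reply is that only treatment is meant. Section 3.1 belongs to the chapter on dose modification, Section 5 is headed as cessation of trial therapy, and no passage expressly stops follow-up. Section 6.1 does not list removal as a censoring reason, so, applied as written, it keeps such patients under observation until an event or study end. This stands in part. A reader might infer that the protocol orders DFS outcomes to be discarded, and the documents do not go that far. They leave two readings open and do not choose between them.

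A reader might also infer that the rule breaches the intent-to-treat definition. It does not: Section 6.3 retains these patients whatever their length of follow-up. The tension is with the purpose of that definition and with the censoring list.

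Nor do the documents show that removals will be more frequent in Arm A. The rule is the same for both arms and no removal rate is given. Section 6.4.4 bases its expectation on neurotoxicity, which Table 2 handles largely by dose changes. On the other side, Section 3.3 names overlapping toxicities. Section 3.4 postpones both drugs together and recommends a second week of waiting, which brings a patient to the two-week threshold. An imbalance is plausible but not established.

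Finally, no passage says that removed patients have a worse prognosis. At equal hazard the bias is zero even with unequal removal. The 8.7% error is a corner case in which every frail Arm A patient, and nobody else in that arm, is removed. The 5.1% at the low end cannot be told from 5% with 2,500 simulations (standard error about 0.44 points).

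**Conclusion.** The point holds as an unreconciled rule that puts outcome data for the primary endpoint at risk. It is not a demonstrated loss of data or a demonstrated bias. Sections 3.1 and 5, taken literally, end observation for a treatment-related reason; Sections 6.1, 6.3 and 6.4.1 need that observation to continue.

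If sites follow the literal reading, the cost in power is modest: from 82.5% to 80.1% at 10%/5% removal and to 77.5% at 20%/10%. With 5% removed in Arm B, 10-15% in Arm A and 1.5-2 times the hazard in removed patients, a null hazard ratio moves to roughly 0.93-0.98, in favour of Arm A. Removal rates, timing and prognosis are all assumptions, since the protocol gives none of them. The change is worth making because it is right under either reading and costs almost nothing.

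**What to change.** Reconcile the passages by stating in Sections 3.1 and 5 that removal or discontinuation refers to trial treatment only. Add that every randomised patient stays in follow-up for relapse, survival and late toxicity until study end or withdrawal of consent, at the intervals in Section 2.1 and with the assessments in Section 2.2.4. That matches the two censoring reasons in Section 6.1, so the list there needs no new entry.

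The two-week rule and the handling of noncompliance are left untouched as clinical rules; the sentence concerns only what happens to follow-up.

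The cost is one sentence in two places and a note to sites. The visits are already part of the routine schedule.
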